9.1 Adverse Events

The summary statistics will be produced in accordance with section 7. When calculating the incidence of adverse events, or any sub-classification thereof by treatment each subject will only be counted once and any repetitions of adverse events will be ignored; the denominator will be the total

population size. Incidence of specific AEs will be presented in summary form up to 30 days. For 12 months follow up, all AEs incidences will be summarized.

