4.4 Study Variables

Observations and records of important variables will be assessed according to the following schedule along with acceptable time-windows. Measurements outside scheduled assessment times will be considered protocol deviations.

Notable evaluations include the following:

COPY

For Control subjects:

Procedure/ Interval	Baseline / Enrollment	Immediately prior to reperfusion (PCI)Post-PCI	Catheter Removal	Discharge*	Follow-Up @ 4-6 Days	Follow-Up @ 30 Days (±7 days)	Follow-Up @ 12 months (±14 days)	Unscheduled Visit
Trial Eligibility & Informed Consent	upon arrival to hospital							
Physical Exam and Medical History	X			X				
Catheter Insertion Time	X							
Catheter Removal Time			X					
Temperature Documented	X							
Vital Signs	X							
Blood Studies RBC's, WBC's, Hct, Hgb, Platelets, Neutrophils, Eosinophils	X							
Pro BNP							X	
Lab Studies BUN, Creatinine, Na, K, Ca, Mg, Cl, P, lactic acid, glucose, amylase, lipase	X							
Any Medication Use	X	X	X	X	X	X	X	X
Troponin I or T	Collect at Baseline	Collected only if peak reached	Collected only if peak reached					
12 lead ECG	X							
Adverse Events		X	X	X	X	X	X	X
Cardiac Magnetic Resonance (cMR)					X			
NYHA Assessment							X	X
KCCQ Assessment							X	X

COPY

For Test subjects:

Procedure/ Interval	Baseline / Enrollment	Initiation of Cooling	Immediately prior to reperfusion (PCI)	Maintenance of Target Temp 32 ±1°C	Rewarming to 36°C	Catheter Removal	Discharge	Follow-Up @ 4-6 Days	Follow-Up @ 30 Days (±7 days)	Follow-Up @ 12 months (±14 days)	Unscheduled Visit
Trial Eligibility & Informed Consent	upon arrival to hospital										
Physical Exam and Medical History	X						X				
Anti-Shivering Protocol	X			X ^o							
Cold Saline Infusion		X									
Catheter Insertion Time		X									
Catheter Removal Time						X					
Temperature Documented	X	X	X	every 30 min during 3 hr cooling							
Temperature Data Download						X					
Vital Signs	X	X	X	every 30 min							
Blood Studies RBC's, WBC's, Hct, Hgb, Platelets, Neutrophils, Eosinophils	X			upon reaching target temperature	upon reaching normothermia						
Pro BNP										X	
Lab Studies BUN, Creatinine, Na, K, Ca, Mg, Cl, P, lactic acid, glucose, amylase, lipase	X										
Any Medication Use	X	X	X	X	X	X	X	X	X	X	
Troponin I or T	X	Collected only if peak reached	Collected only if peak reached	Collected only if peak reached	upon reaching normothermia, Collected only if peak reached	Collected only if Peak reached					

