12 lead ECG	X										
Adverse Events		X	X	X	X	X	X	X	X	X	
Catheter Access Site Assessment						X	X	X			
Cardiac Magnetic Resonance (cMR) imaging								X			
NYHA Assessment									X	X	
KCCQ Assessment									X	X	

COPY

5 Sample Size

Sample size considerations are based on both the primary effectiveness analysis.

The primary effectiveness analyses is designed to detect a relative reduction of 20% in mean anterior myocardial infarct size (IS), as determined by Cardiac Magnetic Resonance (cMR) imaging at 4-6 days post infarct in the Test Arm (cooling + PCI) compared to the Control Arm (PCI only). The absolute magnitude of a relative reduction of 20% depends on the mean IS in the control arm, which is assumed to be approximately 17 %LV. Therefore, the treatment effect of interest is an absolute difference of 3.5 %LV. Therefore, the treatment effect of interest is an absolute difference of 3.5 %LV.

The null hypothesis is that the mean IS in the Test Arm is equal to the mean IS in the Control Arm. The assumed standard deviation is 12 %LV and the final analysis will be conducted using a two-sided test at the alpha=0.044 level of significance (adjusted for the two interim analyses). Based on these assumptions, the required total sample to detect a mean difference of 3.5 %LV with 80% power is 384 subjects (192 subjects per group). Allowing for a potential dropout rate of 24%, the planned total sample size is 500 subjects (250 subjects per group).

$$H_0: \mu_T = \mu_C$$

$$H_A: \mu_T \neq \mu_C$$

Null hypothesis:

The null hypothesis is that the mean IS in the Test Arm is equal to the mean IS in the Control Arm.

Alternative hypothesis:

The mean %LV in the control arm is not equal to mean of control arm.

This 20% relative reduction is defined as absolute value 3.5 %LV and accounted for in our sample size calculation as treatment effect. This assumption is based on previous studies with anterior infarct size measured with cMR reporting between 17-20% absolute %LV in anterior infarct (**Tables 1 & 2**). Therefore, a relative reduction of 20% can vary depending on the mean infarct size of the control arm. Assuming a representative mean infarct size of ~17% in controls, we assume absolute difference of 3.5 %LV is equivalent to 20% mean anterior infarct size would be an adequate detection limit for effect.

COPY

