8.1 Primary Efficacy Analysis

To evaluate anterior infarct size (%LV) in Control and Treatment Arm, summary statistics will be used; n, mean, standard deviation median, interquartile range, minimum, maximum will be reported. T-test (2-sided) or Wilcoxon rank-sum test (2-sided) will be used as appropriate to calculate p-value after evaluation for normality.

9 Safety Analyses

To summarize incidence of adverse events, summary for all site reported events will be conducted on patient basis on the safety analysis set. Specifically, each patient will be counted once for an event and any repetitions will be ignored; the denominator will be the sample population size. Summaries will be produced by treatment (Test vs. Control) as well as an “All Patients” column. 1-sided Chi-square test or Fisher’s-exact test will be used as appropriate depending on whether number of patients are fewer than 5, in which case Fisher’s exact test will be used.

Only deviations from the aforementioned analytical and summary approaches will be noted in the subsequent subsections of section 9.

The only summarized variable is MACE, which is also a composite endpoint.

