Association of infarct size with covariates	ITT and PP	Association with covariates including age, BMI, sex, pre-TIMI flow, post-TIMI flow, DTB, Ischemic time, and temperature at PCI	4-6 day	NA	p-value
NYHA classification at 12 months	ITT	NYHA Classification	12 months	Treatment	x (p%), p-value
KCCQ summary at 12 months	ITT	KCCQ overall summary score and KCCQ clinical summary score	12 months	Treatment	n, mean, SD, median, min, max, p-value

COPY

NT-proBNP summary at 12 months	ITT	NT-proBNP	12 months	Treatment	n, mean, SD, median, IQR, min, max, p-value
Clinical outcome summary (death, MI re-infarction, or TVR at 30 days)	Safety analysis set	MACE (Primary Safety)	30-days	Randomization	x (p%), p-value
Clinical components of mace summary	Safety analysis set	Additional Safety Endpoints	30 days	Randomization	x (p%), p-value
Subjects with serious adverse events summary within 30 days	Safety analysis set	All Serious Adverse Events	30 days	Randomization	x (p%), p-value
Subjects with non-serious adverse events summary within 30 days	Safety analysis set	All Non-Serious Adverse Events	30 days	Randomization	x (p%), p-value
Subjects with serious adverse events summary within 12 months	Safety analysis set	All Serious Adverse Events	12 months	Randomization	x (p%), p-value
Subjects with non-serious adverse events summary within 12 months	Safety analysis set	All Non-Serious Adverse Events	12 months	Randomization	x (p%), p-value
Subjects with serious adverse events of interest within 30 days	Safety analysis set	Serious adverse events of interest	30 days	Randomization	x (p%), p-value
Subjects with death and stent thrombosis within 12 months	Safety analysis set	Death and Stent Thrombosis	12 months	Randomization	x (p%), p-value
DAPT and Anti-Thrombotic Medication	ITT	DAPT and Anti-Thrombotic Medications used	Baseline	Randomization	x (p%), p-value

COPY

Listing of Listings

Title	Population	Display Variables	Time Point	Sort Variable
Subjects not cooled	ITT	Randomization, Subject ID, Reason for not cooling	Baseline	Randomization
Protocol Deviations	ITT	Reasons for deviation	Baseline, 4-6 day, 30 days, 12 months	Randomization, Subject ID
Device Deficiency	ITT	Device type, device disposition, deficiency description	Baseline	Randomization, Subject ID
Serious Adverse Events	ITT	Adverse Event Number, Adverse Event, Adverse event start date, Outcome, Procedure relatedness, Device relatedness	Baseline, 4-6 day, 30 days, 12 months	Randomization, Subject ID, AE number

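### Non-serious AE incidence is compared between arms with p-values although access site, blood counts and vital signs are scheduled after baseline in the Test arm only, so the comparison is open to ascertainment bias

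*SAP*

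**What the plan says.** Section 4.4 of the SAP gives each arm its own schedule.

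- Test: the row "Catheter Access Site Assessment" carries three marks, which read as catheter removal, discharge and days 4-6. Blood counts are taken at baseline, again "upon reaching target temperature", and once more at normothermia. Vital signs are taken at baseline, at cooling initiation, before PCI and every 30 minutes during maintenance.
- Control: under "For Control subjects" there is no access-site row, although catheter insertion and removal times are recorded. Vital signs and blood studies each have a single mark, at baseline.

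The opening of Section 9 says that a "summary for all site reported events will be conducted on patient basis on the safety analysis set", and it names a "1-sided Chi-square test or" Fisher's exact test. Section 9.1 sets the counting rule: "When calculating the incidence of adverse events, or any sub-classification thereof by treatment each subject will only be counted once", with repeat events ignored. The table list in Section 13 includes "Subjects with non-serious adverse events summary within 30 days" and a matching 12-month table, both by randomised arm with a p-value. Section 4.3 says that investigator and subject are not blinded.

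**The concern.** A once-per-subject incidence depends on the chance that at least one event is found and reported. For events found mainly by looking, such as a minor haematoma, an asymptomatic fall in platelets or a brief blood pressure change, that chance cannot fall as scheduled checks are added. Here the extra checks belong to one arm. An excess of such events in Test could be a device effect, a surveillance effect or both, and the planned tables cannot tell these apart. The 12-month table also contains the early events, so an early imbalance carries through to it.

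A p-value on the pooled count could therefore be read as evidence of device harm when part of the difference is surveillance. A real excess could equally be dismissed as artefact.

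**Working it through.** **Scheduled post-baseline assessments, from the two grids in Section 4.4**

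| Assessment | Test | Control |
|---|---|---|
| Access site | 3 | no row |
| Blood counts | 2 | 0 |
| Vital signs | initiation, pre-PCI, every 30 min | 0 |

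The grids were flattened from PDF, so exact column positions in the Test grid carry some uncertainty. The baseline-only Control rows and the missing Control access-site row are clear.

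**What the SAP does with the difference.** Sections 9, 9.1 and 13 neither restrict the non-serious AE tables to events found at common assessments nor caveat the p-values. Sections 9.3 and 9.4 discuss blood chemistry and vital signs at baseline only.

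**What the SAP does not give.** It states no expected non-serious AE rate, no power for this comparison and no detection rates, so there is no plan figure to reproduce. The following is an illustration on assumed inputs.

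Assume 250 subjects per arm (the planned size in Section 5), a one-sided 0.05 test for excess in Test, and the same true incidence p = 20% in both arms of events that depend on checks. Detection is dC in Control and dT in Test. Then a = p × dC, b = p × dT, m = (a + b)/2, and

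- SE0 = √(2m(1 − m)/250)
- SE1 = √((a(1 − a) + b(1 − b))/250)
- rejection probability = Φ(((b − a) − 1.645 × SE0)/SE1)

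Example with dC = 80% and dT = 90%: a = 0.16, b = 0.18, m = 0.17, SE0 = √(2 × 0.17 × 0.83/250) = 0.0336, and SE1 is the same to four decimals. Then (0.02 − 1.645 × 0.0336)/0.0336 = −1.05, which gives 15%.

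That figure treats the whole count as dependent on checks. In the pooled table a subject with any other non-serious AE is already counted. If a share g of subjects in each arm has another AE, independently, then a and b become 1 − (1 − g)(1 − a) and 1 − (1 − g)(1 − b). With g = 60% the example becomes 1 − 0.4 × 0.84 = 0.664 against 1 − 0.4 × 0.82 = 0.672, and rejection falls to 7%.

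| Detection, Control vs Test | g = 0 | g = 20% | g = 60% |
|---|---|---|---|
| 80% vs 80% | 5% | 5% | 5% |
| 80% vs 90% | 15% | 10% | 7% |
| 80% vs 100% | 32% | 19% | 10% |
| 60% vs 90% | 59% | 31% | 14% |

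The false-positive rate stays at 5% when detection is equal, rises when it is not, and is pulled back towards 5% as other AEs fill the count. The table shows direction and dilution only. It does not estimate the bias in this trial.

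**The case against.** A reader might infer from the grids that non-serious AE rates in Test are higher by construction. The documents do not support that. AE collection is scheduled at the shared visits in both arms, events are site-reported, and no rule turns a vital sign or blood count into an AE. The grids list trial assessments and do not say that Control patients go unobserved after PCI. Higher detection in Test is a risk, not a certainty.

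Other parts of the opposing case also stand:

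- Large inflation figures need strong detection differences applied to the whole count. No SAP figure supports those inputs, and dilution shrinks the effect.
- Section 9 does not state the direction of its one-sided test, and Section 6.4 says enrolment was never completed. Both the tested direction and 250 per arm are therefore assumptions.
- Access-site events may be real effects of the cooling catheter. Removing the test for those terms altogether would be a genuine loss.
- The non-serious AE listing shows start date and procedure and device relatedness, so a reader could trace these events by hand.
- The counting rule in Section 9.1 is ordinary and not wrong in itself.

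What these points do not answer is that asking about events at a shared visit does not replace a scheduled measurement. Counting each subject once prevents double counting but does not equalise the chance of a first detection. With reporting left to the judgement of unblinded sites, nothing in the SAP protects against unequal ascertainment.

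**Conclusion.** The point holds as a minor one. The schedules are unequal for three kinds of assessment, non-serious AEs are compared by arm with p-values, and the SAP is silent on the consequence. The comparison is open to ascertainment bias against Test. How large that bias is cannot be said from the SAP: it depends on detection rates that are not given, it is diluted in the pooled count, and it is nil if routine care finds the same events in Control.

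Non-serious AEs are neither the primary safety endpoint nor among the additional safety endpoints in Section 3.2, and no success rule uses them. This argument does not touch the MACE comparison.

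**What to change.** In Sections 9.1 and 13:

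1. Keep the all-event AE tables by arm as planned.
2. Pre-list the access-site, blood-count and vital-sign AE terms, deciding borderline terms such as bleeding and hypotension explicitly. Because the trial is open-label, fix the list without sight of event counts by arm.
3. Add to the non-serious AE tables, at 30 days and 12 months, a between-arm comparison limited to events outside that set. The set consists of listed terms with onset up to the day 4-6 visit.
4. Show the set separately by arm, with a footnote that its scheduled assessment differed between arms, so an excess in Test may reflect device effect, surveillance or both.

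The cost is one extra table and a pre-specified term list. AE term and start date are already among the listing variables in Section 13, so no new data are needed. No event is hidden, because the all-event tables and their p-values remain.

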9.2 Deaths, Serious Adverse Events and other Significant Adverse Events

The summary statistics will be produced in accordance with section 7.

9.3 Clinical Laboratory Evaluations

A Core Lab is employed to ensure that difference between study centres are minimized for measurement of IS, which is the primary endpoint. For blood chemistry at baseline, while summary statistics including mean, median, standard deviation, and range will be presented, the CRF will also note whether the value is clinically significant or not to ensure that normal ranges have been provided by all centres and that outliers are noted.

9.4 Other Safety Measures

Vital signs are taken at baseline and reviewed and queried as appropriate regarding whether values are reasonable and compatible with life. DSMB will convene periodically to review safety data summaries.

10 Other Analyses

KCCQ, , and NT-proBNP at 12 months patients will be presented in summary form only for mean, median, standard deviation, interquartile range, and range. No formal statistical analyses will be conducted.

11 Reporting Conventions

P-values ≥ 0.001 will be reported to 3 decimal places; p-values less than 0.001 will be reported as “ <0.001 ”. The mean, standard deviation, and quantiles will be reported to the same precision for decimal place as the original data.

12 Technical Details

Statistical analyses will be conducted using SAS and R and other statistical software as appropriate. Citations will be provided for all statistical software used.

Verification and validation of the primary efficacy and safety analyses will be provided by independent programming and analyses by a second analyst, who will also be provided an overview of the entire analyses. The second analyst will also verify code and results selected at random.

COPY

13 Listings of Tables, Listings and Figures

Listing of Tables

Table Title	Population	Endpoint	Time Point	Covariates or Subgroups	Summary Statistics
Randomization and Follow-ups	ITT	Subject disposition through the trial	Baseline, 4-6 day, 30 days, 12 months	Randomization	x (p%)
Protocol Deviations	ITT	Protocol deviations reported	Baseline, 4-6 day, 30 days, 12 months	Randomization	x
Baseline demographic and clinical characteristics	ITT	Demographics and clinical baseline variables	Baseline	Randomization	n, mean, SD, median, IQR, min, max, x (p%), p-value
Medical History	ITT	Subject medical history	Baseline	Randomization	x (p%), p-value
Treatment Description	ITT	Treatment variables	Baseline	Randomization	n, mean, SD, median, IQR, min, max, p-values
Baseline ECG and Angiographic Findings	ITT	Angiographic and Baseline ECG variables	Baseline	Randomization	x (p%), p-value
Cooling Procedure	ITT	Anti-shivering management, shivering, temperature at baseline, temperature at initiation of cooling, temperature at wire-crossing, duration of cooling phases, catheter indwell time, total volume of cold saline	Baseline	Randomization	n, mean, SD, median, IQR, min, max, x (p%), p-value
cMR Results	ITT and PP	cMR findings	4-6 day	Randomization and Treatment	n, mean, SD, median, IQR, min, max, p-value
Association of infarct size with covariates	ITT and PP	Association with covariates including age, BMI, sex, pre-TIMI flow, post-TIMI flow, DTB, Ischemic time, and temperature at PCI	4-6 day	NA	p-value
NYHA classification at 12 months	ITT	NYHA Classification	12 months	Treatment	x (p%), p-value
KCCQ summary at 12 months	ITT	KCCQ overall summary score and KCCQ clinical summary score	12 months	Treatment	n, mean, SD, median, min, max, p-value

COPY

NT-proBNP summary at 12 months	ITT	NT-proBNP	12 months	Treatment	n, mean, SD, median, IQR, min, max, p-value
Clinical outcome summary (death, MI re-infarction, or TVR at 30 days)	Safety analysis set	MACE (Primary Safety)	30-days	Randomization	x (p%), p-value
Clinical components of mace summary	Safety analysis set	Additional Safety Endpoints	30 days	Randomization	x (p%), p-value
Subjects with serious adverse events summary within 30 days	Safety analysis set	All Serious Adverse Events	30 days	Randomization	x (p%), p-value
Subjects with non-serious adverse events summary within 30 days	Safety analysis set	All Non-Serious Adverse Events	30 days	Randomization	x (p%), p-value
Subjects with serious adverse events summary within 12 months	Safety analysis set	All Serious Adverse Events	12 months	Randomization	x (p%), p-value
Subjects with non-serious adverse events summary within 12 months	Safety analysis set	All Non-Serious Adverse Events	12 months	Randomization	x (p%), p-value
Subjects with serious adverse events of interest within 30 days	Safety analysis set	Serious adverse events of interest	30 days	Randomization	x (p%), p-value
Subjects with death and stent thrombosis within 12 months	Safety analysis set	Death and Stent Thrombosis	12 months	Randomization	x (p%), p-value
DAPT and Anti-Thrombotic Medication	ITT	DAPT and Anti-Thrombotic Medications used	Baseline	Randomization	x (p%), p-value

COPY

Listing of Listings

Title	Population	Display Variables	Time Point	Sort Variable
Subjects not cooled	ITT	Randomization, Subject ID, Reason for not cooling	Baseline	Randomization
Protocol Deviations	ITT	Reasons for deviation	Baseline, 4-6 day, 30 days, 12 months	Randomization, Subject ID
Device Deficiency	ITT	Device type, device disposition, deficiency description	Baseline	Randomization, Subject ID
Serious Adverse Events	ITT	Adverse Event Number, Adverse Event, Adverse event start date, Outcome, Procedure relatedness, Device relatedness	Baseline, 4-6 day, 30 days, 12 months	Randomization, Subject ID, AE number
Non-Serious Adverse Events	ITT	Adverse Event Number, Adverse Event, adverse event start date, Outcome, Procedure relatedness, Device relatedness	Baseline, 4-6 day, 30 days, 12 months	Randomization, Subject ID, AE number
CEC adjudication results of MACE at 30 days	Safety analysis set	CEC adjudication of MACE	30 days	Subject ID, AE number

Listing of Figures

Title	Population	Type of graph	Horizontal Variables	Vertical Variables	Groupings	Statistics	Facets
CONSORT Diagram	ITT	Flow chart					NA
Temperature Over Time	ITT	Line	Time	Temperature	Randomization	Mean, SD	NA
Infarct Size	ITT and PP	Boxplot with Scatter	Treatment	Infarct Size (LV%)	Treatment	Mean, Median, IQR, absolute difference, relative difference, p-value	NA
Ejection Fraction	ITT and PP	Boxplot with Scatter	Treatment	Ejection Fraction (%)	Treatment	Mean, Median, IQR, absolute difference, relative difference, p-value	NA
Distribution of Ischemic time with infarct size	ITT and PP	Scatterplot	Ischemic time	Infarct size at 4-6 days	Treatment	NA	NA
Distribution of Ischemic time with infarct size	ITT and PP	Scatterplot	Ischemic time	Infarct size at 4-6 days	Treatment	N, 95% CI, beta coefficient, p-value, R ² , adjusted R ²	NA

COPY

14 References

¹ Yellon DM, Hausenloy DJ. Myocardial reperfusion injury. *N Engl J Med* 2007; 357(11):1121-1135.

² Negovsky VA. Postresuscitation disease. *Crit Care Med* 1988; 16:942-946.

³ Bolli R. Does Lethal Myocardial Reperfusion Injury Exist? A Controversy that is Unlikely to Be Settled in our Lifetime. *J Thromb Thrombolysis* 1997; 4(1):109-110.

⁴ Colbourne F, Sutherland G, Corbett D. Postischemic hypothermia. A critical appraisal with implications for clinical treatment. *Mol Neurobiol* 1997; 14(3):171-201.

⁵ Duncker DJ, Klassen CL, Ishibashi Y, Herrlinger SH, Pavek TJ, Bache RJ. Effect of temperature on myocardial infarction in swine. *Am J Physiol* 1996; 270(4 Pt 2):H1189-H1199.

⁶ Miki T, Liu GS, Cohen MV, Downey JM. Mild hypothermia reduces infarct size in the beating rabbit heart: a practical intervention for acute myocardial infarction? *Basic Res Cardiol* 1998; 93(5):372-383.

⁷ Dae MW, Gao DW, Ursell PC, Stillson CA, Sessler DI. Safety and efficacy of endovascular cooling and rewarming for induction and reversal of hypothermia in human-sized pigs. *Stroke* 2003; 34(3):734-738

